11.1.2 Solicited Adverse Events

A solicited AE is one that is prelisted in the electronic diary card (paper diary card could be used as back up).

In this study, fever, vomiting, crying abnormal, drowsiness, loss of appetite, diarrhea and irritability will be solicited for 7 days after each study vaccine administration.

Subjects' parent(s) and/or guardian(s) will be provided with an electronic diary. A paper diary card will be provided as back up. This will include the definitions of mild, moderate and severe AEs, as described in Table 4, to facilitate the assessments of the level of functional impairment for each experienced AE. Any solicited AEs reported in the diary will be reviewed by the Investigator during the phone calls or on-site visits that will be scheduled 7 days after each dose of study vaccine.

Axillary temperature should be measured in the evening using the thermometer provided. Should additional temperature measurements be performed at other times of day, the highest temperature must be recorded in the electronic diary.

11.1.3 *Serious Adverse Events*

The Investigator will be responsible for recording and reporting within 24 hours and according to regulatory timelines all SAEs observed during the study (treatment and follow-up) period.

An SAE, experience or reaction, is any untoward medical occurrence (whether considered to be related to study drug or not) that at any dose:

- Results in death.
- Is life-threatening (the subject is at a risk of death at the time of the event; it does not refer to an event which hypothetically might have caused death if it were more severe).
- Requires inpatient hospitalization or prolongation of existing hospitalization: Hospital admissions and/or surgical operations planned before or during a study are not considered AEs if the illness or disease existed before the subject was enrolled in the study, provided that it did not deteriorate in an unexpected way during the study.
- Results in persistent or significant disability/incapacity.
- Is a congenital abnormality/birth defect detected only after study inclusion.

11.1.4 *Important Medical Event*

The Investigator will be responsible for recording and reporting within 24 hours and according to regulatory timelines all IMEs observed during the study (treatment and follow-up) period.

IMEs are medically significant events that do not meet any of the SAE criteria above, but require medical or surgical consultation or intervention to prevent this event to become one of the serious outcomes listed in the SAE definition above. Examples of IMEs include allergic bronchospasm requiring intensive treatment in an emergency room or at home, blood dyscrasias (e.g., neutropenia or anemia requiring blood transfusion, etc.) or convulsions that do not result in hospitalization. Although IMEs are not SAEs, they are processed in the same way as SAEs. Every aspect described for SAEs (including study objectives and endpoints) also applies to an IME.

11.2 INTENSITY OF ADVERSE EVENTS

11.2.1 *Solicited Adverse Events*

The intensity of the solicited AEs will be assessed using the scale provided in Table 4.

Table 4 Intensity scales for solicited symptoms

Adverse Event	Intensity grade	Parameter
Fever	0	<37.5°C
	1 (mild)	37.5°C to 38.0°C
	2 (moderate)	38.1°C to 39.0°C
	3 (severe)	>39.0°
Vomiting	0	None
	1 (mild)	1 episode per 24 hours
	2 (moderate)	2 - 5 episodes per 24 hours
	3 (severe)	≥6 episodes per 24 hours or requiring parenteral hydration
Abnormal crying	0	None
	1 (mild)	<1 hour
	2 (moderate)	1 - 3 hours
	3 (severe)	>3 hours
Drowsiness	0	None
	1 (mild)	Sleepier than usual or less interested in surroundings
	2 (moderate)	Not interested in surroundings or did not wake up for a feed/meal
	3 (severe)	Sleeping most of the time or difficult to wake up
Loss of appetite	0	None
	1 (mild)	Eating less than normal
	2 (moderate)	Missed 1 or 2 feeds/meals completely
	3 (severe)	Refuses ≥3 feeds/meals or refuses most feeds/meals
Irritability	0	None
	1 (mild)	Easily consolable
	2 (moderate)	Requiring increased attention
	3 (severe)	Inconsolable
Diarrhea	0	None
	1 (mild)	An increase by 3 bowel movements (above normal or baseline) that are looser than normal per day, with no limitation to activities of daily living
	2 (moderate)	An increase by 4–6 bowel movements (above normal or baseline) that are looser than normal per day, or an increase of 3–6 bowel movements per day (above normal or baseline) that are looser than normal, with some interference with activities of daily living
	3 (severe)	An increase by 7 or more bowel movements per day (above normal or baseline) that are looser than normal per day, or an increase by 3 or more bowel movements per day (above normal or baseline) that are looser than normal, with incapacitating symptoms or interference with activities of daily living, or loose stools with visible red or tarry black blood in stool

11.2.2 *Unsolicited Adverse Events*

The investigator will assess the incidence and maximum intensity that occurred over the duration of the event for all unsolicited AEs recorded during the study. The assessment will be based on the investigator's clinical judgment.

The intensity should be assigned to one of the following categories:

1 (mild)	= An AE which is easily tolerated by the subject, causing minimal discomfort and not interfering with everyday activities.
2 (moderate)	= An AE which is sufficiently discomforting to interfere with normal everyday activities.
3 (severe)	= An AE which prevents normal, everyday activities (in adults, such an AE would, for example, prevent attendance at work and would necessitate the administration of corrective therapy.)
4 (life-threatening)	= An AE that puts the subject at risk of death
5 (fatal)	= An AE that results in death

[figure not shown]
An AE that is assessed as Grade 3 (severe) should not be confused with a SAE. Grade 3 is a category used for rating the intensity of an event; and both AEs and SAEs can be assessed as Grade 3. An event is defined as 'serious' when it meets one of the pre-defined outcomes as described in Section 11.1.3, or when it is of Grade 4 or 5.

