3.2 SECONDARY ENDPOINTS

Immunogenicity:

- Geometric mean and median titers of type 2 polio neutralizing antibodies Day 0 and 28 days after the second dose of nOPV2 when administered 1, 2, or 4 weeks apart.
- Cumulative fold-rise (from Day 0) in titers of type 2 polio neutralizing antibodies 28 days after the second dose of nOPV2 when administered 1, 2, or 4 weeks apart. Cumulative fold-rise will be computed relative to the expected level of maternally-derived antibody titers in accordance with the seroconversion definition.
- Fold-rise (from post-dose-1 level) in titers of type 2 polio neutralizing antibodies 28 days after the second dose of nOPV2 when administered 1, 2, or 4 weeks after dose-1. This fold-rise will be computed from the level attained following the first dose, with the pre-dose-2 serum sample.
- Seroprotection rate to poliovirus type 2, at Day 0 and 28 days after the second dose of nOPV2 when administered 1, 2, or 4 weeks apart.
Seroprotection rate is defined as the percentage of subjects with type 2-specific antibody titers $\geq 1:8$.
- Geometric mean and median titers of type 2 polio neutralizing antibodies 1, 2, and 4 weeks after 1 dose of nOPV2.
- Fold-rise in titers of type 2 polio neutralizing antibodies 1, 2, and 4 weeks after 1 dose of nOPV2. This fold-rise will be computed relative to the expected level of maternally-derived antibody titers in accordance with the seroconversion definition.
- Seroconversion rate 1, 2, and 4 weeks after 1 dose of nOPV2.
- Seroprotection rate 1, 2, and 4 weeks after 1 dose of nOPV2.

Safety:

- Incidence of SAEs and IMEs as of the informed consent signature date and throughout the study period in all groups by severity and causal association.
- Incidence of mild, moderate and severe solicited AEs (fever, vomiting, abnormal crying, drowsiness, loss of appetite, diarrhea and irritability) for 7 days after each dose of study vaccine in all groups.
- Incidence of mild, moderate and severe unsolicited AEs for 28 days after each dose of study vaccine by causal association in all groups.

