5.4 CONTRAINDICATIONS TO FURTHER VACCINATION

The following AEs constitute absolute contraindications to further administration of the study vaccine:

- SAE, severe adverse event (grade 3) or IME after vaccination considered to be consistent with a causal association to the study vaccine.
- Known hypersensitivity to any component of the vaccine or any antibiotic or severe reaction following previous administration of the vaccine.
- Acute severe febrile illness on the day of vaccination deemed by the Investigator to be a contraindication for vaccination.
- Diagnosis between 2 visits of any of the following medical conditions:
 - o Uncontrolled severe chronic disease (see above under exclusions).
 - o Coagulopathy.
 - o Congenital or acquired immunodeficiency syndrome.
 - o Acute flaccid paralysis (to be investigated as a SAE).

If any of these AEs occur during the study, the subject should not receive the second dose of vaccine but may continue other study procedures at the discretion of the Investigator. The subject will be followed until resolution of the event and to determine the immune response.

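### The moderate and severe diarrhea rows of Table 4 overlap and no rule says which grade counts, so the moderate/severe split for this one solicited term is not reproducible

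*Combined protocol and SAP*

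**What the plan says.** Section 11.2.1 makes Table 4 the scale for every solicited event: "The intensity of the solicited AEs will be assessed using the scale provided in Table 4". For diarrhea, grades 2 and 3 can each be reached in more than one way:

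- Grade 2, count only: "An increase by 4–6 bowel movements (above normal or baseline) that are looser than normal per day".
- Grade 2, count plus function: "an increase of 3–6 bowel movements per day (above normal or baseline) that are looser than normal, with some interference" in daily activities.
- Grade 3, count only: seven or more extra loose stools a day.
- Grade 3, count plus function: "or an increase by 3 or more bowel movements per day (above normal or baseline", for stools "that are looser than normal, with incapacitating symptoms or interference with activities of daily living".
- Grade 3, visible blood in loose stools.

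Section 11.1.2 carries these definitions into the parents' diary and has the investigator review the entries at a contact 7 days after each dose. The grades feed a secondary safety endpoint in section 3.2, which begins: "Incidence of mild, moderate and severe solicited AEs (fever, vomiting, abnormal crying, drowsiness, loss of appetite, diarrhea and irritability". Section 5.4 also uses the severe grade. Among the bars to further study vaccine it lists: "SAE, severe adverse event (grade 3) or IME after vaccination considered to be consistent with a causal association to the study vaccine".

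**The concern.** A severity scale should give one grade for one presentation. Here the grade 2 functional clause covers 3–6 stools and the grade 3 functional clause covers three or more. The only thing separating them is the word 'some', which grade 2 has and grade 3 lacks. A parent and an investigator, or two sites, could each apply Table 4 correctly and report different grades for the same infant.

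What is at stake is the count of moderate and of severe diarrhea by group and dose. Diarrhea is a relevant term, since section 1.3.1 says that the vaccine virus multiplies in the gut. Grade 3 also appears in section 5.4, so the grade might bear on conduct as well as on the tables.

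**Working it through.** **Inputs.** The rules come from Table 4 and the group size of 300 from section 4.1. The plan gives no expected rate of diarrhea by grade, so there is no plan figure to reproduce. The sample size in section 10.2 rests on seroconversion and does not use these grades.

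**Rules as logical conditions.** Let k be the number of extra loose stools per day and f the functional effect (none, some, incapacitating). Visible blood is set aside as a separate route to grade 3.

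- Grade 1: k = 3 and f = none.
- Grade 2: 4 ≤ k ≤ 6, or 3 ≤ k ≤ 6 with f = some.
- Grade 3: k ≥ 7, or k ≥ 3 with a qualifying f.

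The grade 3 wording allows two readings of a qualifying f. On the literal reading, any interference qualifies. On the other, 'incapacitating' governs both nouns and only incapacitating effects qualify.

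| Extra stools | Function | Grades met, literal | Grades met, 'incapacitating' governs both |
|---|---|---|---|
| 3 | none | 1 | 1 |
| 3 | some | 2 and 3 | 2 |
| 3 | incapacitating | 3 | 3 |
| 4–6 | none | 2 | 2 |
| 4–6 | some | 2 and 3 | 2 |
| 4–6 | incapacitating | 2 and 3 | 2 and 3 |
| 7 or more | any | 3 | 3 |

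Each reading leaves at least one presentation with two grades.

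**Is there a rule for double matches?** The only maximum-intensity sentence is in section 11.2.2. It covers unsolicited events, and it concerns the peak over an event's duration. Suppose a highest-grade rule were borrowed. On the literal reading, every case in the second grade 2 clause would become grade 3, so that clause could never be used. On the other reading, every row would have one grade and every clause would be used. The protocol states neither the rule nor the reading.

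**Comparison within the protocol.** The unsolicited scale in section 11.2.2 puts interference with everyday activities at grade 2 and prevention of them at grade 3. Table 4 lists unqualified interference at grade 3 for diarrhea, so the same idea sits at different grades in the two scales.

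**Possible size.** Infants per group and dose who could be counted under either grade = 300 × assumed share with the ambiguous pattern:

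- 1%: 300 × 0.01 = 3
- 2%: 300 × 0.02 = 6
- 5%: 300 × 0.05 = 15

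The number with any diarrhea does not change.

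**The case against.** The best defence is that Table 4 is an ordered scale. Its functional terms for diarrhea rise from no limitation, through some interference, to incapacitating, so it is natural to let 'incapacitating' cover both nouns. Readers of such scales also tend to take the highest grade met. The vomiting row seems built that way, since parenteral hydration makes an event severe whatever the number of episodes. With both conventions the diarrhea rows give one grade throughout. The investigator also reviews the diary, so parents do not grade alone. All three groups receive the same vaccine under the same scale, and section 10.1.5 makes the safety analysis descriptive.

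Much of this stands. It shows that a coherent scale is close at hand and that the effect on the trial's conclusions is small. But the defence needs two conventions, and the protocol writes down neither. On the plain wording, the highest-grade convention alone would make one grade 2 clause redundant. The investigator reviews against the same definitions and has no further rule to apply.

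A reader might infer that, because section 6.6 makes the trial open-label, the overlap biases the comparison between intervals. The documents show no mechanism by which knowing the group would shift the grading of diarrhea in one direction.

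**Conclusion.** The overlap is real. On the literal reading, 3–6 extra loose stools with some interference meets grades 2 and 3. On the alternative reading, 4–6 stools with incapacitating symptoms still does. With no rule for double matches, the moderate/severe split of diarrhea cannot be reproduced from the protocol. If 1–5% of infants per dose had the ambiguous pattern, 3–15 per group of 300 could fall in either grade. That share is an assumption, not a figure from the documents.

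Three stronger readings are not supported:

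- A reader might infer that the severity endpoint as a whole is undefined. The fault is one boundary of one of seven terms. Any-grade diarrhea, grade 1, 4–6 stools without interference and seven or more stools are not touched by it. Nor are the other six terms or the primary endpoint.
- A reader might infer that the ambiguous cases could outnumber the true severe ones. The documents give no count or rate for severe diarrhea, so the comparison cannot be made.
- A reader might infer that one stool pattern would lead to two different decisions on the second dose. Section 5.4 also requires a causal association. Section 11.3 requires causality assessment for unsolicited events, SAEs and IMEs, not for solicited events as such, while section 11.6 asks for an opinion on relationship without drawing that line. Whether non-serious solicited diarrhea reaches the section 5.4 rule is therefore unclear. If it does, only diarrhea after the first dose could matter.

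**What to change.** 1. Reconcile the grade 2 and grade 3 diarrhea rows of Table 4 so that they are mutually exclusive, under the count clauses as well as the functional ones. Where the boundary lies is for the sponsor to decide.
2. State one rule for a solicited event that meets two grades, and apply it both at investigator review and in programming.
3. Carry identical text into the electronic and paper diaries and into the SAP, which section 10.1 says will be finalized before database lock. The diary text needs to be settled before enrolment, because parents use it.
4. Reconcile sections 5.4, 11.3 and 11.6 so that it is clear whether and how the grade 3 rule in 5.4 applies to solicited diarrhea.

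The cost is a text edit to the protocol, diary and SAP. The downside is slightly less direct comparability of diarrhea severity with any earlier study that used the present wording. The sample size and the primary analysis do not change.

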11.3 CAUSALITY ASSESSMENT

The investigator is obligated to assess the relationship between investigational vaccine and the occurrence of each unsolicited AE/SAE/IME. The investigator will use clinical judgement to determine the relationship. Alternative plausible causes, such as natural history of the underlying diseases, concomitant therapy, other risk factors, and the temporal relationship of the event to the investigational vaccine will be considered and investigated. The investigator will also consult the Investigator's Brochure to determine his/her assessment.

Causality should be assessed by the investigator using AEFI causality algorithm developed by WHO for individual AEFI evaluation¹⁸. When appropriate information is available the investigator should arrive to the following possible conclusions:

Figure 1. Adverse Event Following Immunization Causality Algorithm

*B1 : Potential signal and maybe considered for investigation

SAEs considered to be causally related to the vaccination will be termed SARs.

If an event meets the criteria to be determined as ‘serious’ (see Section 11.1.3), additional examinations/tests will be performed by the investigator in order to determine ALL possible contributing factors for each SAE.

Possible contributing factors include:

- Medical history.
- Other medication.
- Protocol required procedure.
- Other procedure not required by the protocol.
- Lack of efficacy of the vaccine, if applicable.
- Erroneous administration.
- Other cause (specify).

11.4 ACTION TAKEN REGARDING THE STUDY VACCINE

The action taken towards the study vaccine must be described as follows:

- Permanently discontinued.
- Stopped temporarily.
- No action taken.
- Not applicable.

11.5 OUTCOME

The outcome of each AE must be rated as follows:

- Recovered/resolved.

- Recovering/resolving.
- Not recovered/not resolved.
- Recovered with sequelae/resolved with sequelae.
- Fatal (SAEs only).

11.6 RECORDING OF ADVERSE EVENTS

All AEs occurring within 28 days of each vaccination and all SAEs occurring during the clinical investigation must be documented in the source documents and on the AE forms of the eCRF. The Investigator will inquire about the occurrence of AEs/SAEs at every visit/contact during the study.

Whenever possible, diagnoses should be given when signs and symptoms are due to a common etiology (e.g., cough, runny nose, sneezing, sore throat, and head congestion should be reported as “upper respiratory infection”). Investigators must record their opinion concerning the relationship of the (S)AE to the study vaccine in the source documents and on the eCRF. All measures required for (S)AE management must be recorded in the source documents and reported according to Sponsor’s instructions.

All AEs occurring at any time during the study will be followed by the Investigator until satisfactory resolution (e.g., value back to baseline value) or stabilization or until final database lock. If necessary, in order to obtain additional information to ensure safety to the subject, additional blood and urine samples may be taken at the discretion of the Investigator. Certain long-term AEs related to therapy cannot be followed until resolution within the setting of this study. In these cases follow-up will be the responsibility of the treating physician.

11.7 REPORTING OF SERIOUS ADVERSE EVENTS TO THE SPONSOR

All SAEs independent of the circumstances or suspected cause must be reported on a SAE Form by the Investigator to the Sponsor, the Contract Research Organization (CRO), and to Assign Safety Desk (contractor for pharmacovigilance) within 24 h of their knowledge of the event, preferably by fax ([contact]).

The SAE form should include a clearly written narrative describing signs, symptoms, and treatment of the event, diagnostic procedures, as well as any relevant laboratory data and any sequelae, in order to allow a complete medical assessment of the case and independent determination of the possible causality.

Follow-up and outcomes should be reported for all subjects who experience an SAE. It is critical that the information provided on the SAE Form matches the information recorded in the source documents and on the eCRF for the same event.

Copies of additional laboratory tests, consultation reports, postmortem reports, hospital case reports, autopsy reports, and other documents should be sent when requested and applicable. Follow-up reports relative to the subject’s subsequent course must be submitted to the Sponsor and Assign (contractor for pharmacovigilance) until the event has subsided or, in the event of permanent impairment, until the condition stabilizes.

11.8 REPORTING OF SERIOUS ADVERSE EVENTS TO COMPETENT AUTHORITIES/ETHICS COMMITTEES

FIDEC assumes responsibility for appropriate reporting of AEs to the regulatory authorities. FIDEC will also report to the Investigator all SAEs that are unlisted (unexpected) and associated with the use of the vaccine. The Investigator must report these events to the appropriate Independent Ethics Committee/Institutional Review Board (IEC/IRB) that approved the protocol, unless otherwise required and documented by the IEC/IRB.

Adverse event reporting, including suspected unexpected serious adverse reactions (SUSARs), will be carried out in accordance with applicable local regulations.

After termination of the clinical study (determined as the LSLV), any unexpected safety issue that changes the risk-benefit analysis and is likely to have an impact on the subjects who have participated in the study, together with proposed actions, will be reported by the Sponsor to the competent authority(ies) concerned as soon as possible.

11.9 DATA MONITORING COMMITTEE

A DSMB will monitor the safety aspects of this study. The composition and functioning of the Board is documented in the DSMB charter.

12. ETHICAL ASPECTS

12.1 STUDY-SPECIFIC DESIGN CONSIDERATIONS

Potential subjects' parent(s)/guardian(s) will be fully informed of the nature of the study and of the risks and requirements of the study before any study-related assessment will be carried out. During the study, subjects' parent(s)/guardian(s) will be given any new information that may affect their child's decision to continue participation. They will be informed that their child's participation in the study is voluntary and that they may withdraw their child from the study at any time with no reason given and without penalty or loss of benefits to which they or their child would otherwise be entitled. Only subjects' whose parent(s)/guardian(s) are fully able to understand the risks, benefits, and potential AEs of the study and who provide their consent voluntarily will be enrolled in the study.

